Amiloride therapy: In previous clinical trials with higher doses (10 mg) amiloride was well tolerated.¹ Nevertheless, our team of investigators is well aware of the potential side effects (1-10%): dizziness, fatigue headache, hyperkalemia. Subjects will be closely monitored during the drug/placebo treatment intervention. After each safety visit, the PI will review blood pressure and heart rate readings, as well as results of renal function and potassium levels. The treatment will be held in cases of hyperkalemia > 5.5 mEq/L, creatinine increases more than 30% above baseline, hypotension or severe dizziness. If the subject exhibits hyperkalemia or if creatinine increases more than 30% above baseline, the study team will repeat safety labs until they return to baseline. If a subject exhibits potassium > 5.5 mEq/L, creatinine increases more than 30% above baseline, hypotension or severe dizziness on the 5 mg dose, medication will be held for 1 week and a lower dose of amiloride will be started (half of a 5mg tablet). Once the dose of a half of a 5mg tablet has been started, a safety visit will be completed 1 week later. If no clinically significant abnormalities are documented, safety visits will proceed as scheduled for the 5 mg dose. In the event of a severe adverse event the subject will be unblinded to facilitate medical care.

Placebo therapy: The use of placebo and blinding of study team prevents bias of the investigator and study team as well as providing a control for the study. There are two components to the placebo, one being the cellulose found inside the capsule and the other being the gelatin pill capsule used for all study pills being dispensed.

An Investigational New Drug (IND) is not included as part of this protocol because the study medication, amiloride is being used as an FDA approved dose in a population that is not anticipated to have increased risk or decreased acceptability of risk. Lastly, no information will be submitted to the FDA to support a labeling indication, a labeling change, or a change in advertising, as this is not the intent of the current study.

[figure not shown]

Figure 1. Treatment Flow Chart based on management of side effects and adverse events.

III. Recruitment Process

Subjects will be recruited by a number of means.

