- 9. Participation in regular exercise > 3 days/wk per week at a moderate or vigorous intensity
- 10. Pregnancy or lactation in women (or women not using contraceptives)
- 11. Women who plan to become pregnant during the duration of the trial
- 12. Chronic use of NSAIDs
- 13. Potassium level > 5.0 mqE/L at time of screening
- 14. Blood pressure at screening <110/70

VI. Number of Subjects

Men (n=72) and women (n=87) (total=159 overweight/obese subjects) with IR will be recruited for this study. Postmenopausal women are those who have not menstruated for at least **6 months**.^{5,6}

Table 1 presents the estimated sample sizes necessary to test the response to amiloride and compare the

[figure not shown]
Table 1. Repeated- measures design for amiloride treatment	Baseline and treatment cfPWV (m/s)	SD of the Δ	Power	Alph	Calculated sampled size	Final recruitment target 2:1 Amiloride Placebo	
1. Premenopausal women	7.2> 6.2	1.2	90%	0.05	30	34	17
2. Young men (30-50 y)	7.1> 6.6	0.5	90%	0.05	21	24	12
3. Old men (51-70 y)	8.0> 7.5	0.5	90%	0.05	21	24	12
4. Postmenopausal women	8.0> 7.5	0.5	90%	0.05	21	24	12

responses of men and women. We hypothesize that the improvement in carotid femoral pulse wave velocity (cfPWV) in men will be intermediate between the two female groups. Because of the negative effect of estrogen-stimulated ENaC activation, we believe that amiloride will benefit premenopausal women more (a Δ , reduction of 1.0 m/s) than the other groups. Our sample size also allows for a greater variation in the response of premenopausal women due to the effects of reproductive hormones in this group⁷ (SD of the change of 1.2 m/s, **Table 1**). By contrast, we anticipate that the response of post-menopausal women (**Table 1**) will be equal to that of the older men or could even be the lowest of all the groups, given a lesser contribution of estrogen signaling in the activation of ENaC in this population. In summary, the final sample sizes listed below will give 90% power to detect each group's changes in cfPWV.

VII. Study Procedures/Design/Treatment Plan

Planned visits:

Screening visit: Written consent, DOB, gender, ethnic/racial category, height, waist circumference, body weight (history of body weight gain or loss, vital signs, medical history and screening laboratories. Entire visit

is expected to take up to an 1 hour.

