- Visit #7 (20 weeks after starting the medication +/- 6 days): Vital signs, safety questionnaire for side effects, and blood draw for safety laboratories (basic metabolic panel). Entire visit is expected to take up to 30 minutes. If the prior safety visit labs have been within the protocol parameters this visit may be completed as a phone call visit to collect safety questionnaire for side effects and any changes in the subject's health.

Visit #8 (24 weeks after starting the medication +/- 6 days): Vital signs (blood pressure and heart rate), weight, DEXA, waist circumference, safety questionnaire for side effects, and blood draw for safety laboratories (basic metabolic panel, lipid panel, and hemoglobin and hematocrit). Subject will also have assessment of brachial and popliteal artery FMD, cfPWV, femoral artery blood flow and oral glucose tolerance test (OGTT) (amount of blood drawn for safety labs, other biochemistries and OGTT not to exceed 70 mL). OGTT will be done when glucose beverage (75g) is available in a volume within 50ml of what was used in the baseline visit. These will minimize variability of the measurements related to changes in the volume of liquid ingested. Women of childbearing age will undergo a pregnancy test prior to the DEXA scan and withdrawn from study if pregnancy is confirmed. Entire visit is expected to take up to 6 hours.

Additional Safety Visits/unscheduled visits might be scheduled in cases of down titration of amiloride dose. Vital signs, safety questionnaire for side effects, and blood draw for safety labs (amount not to exceed 15mL). Unscheduled visits may also occur if safety lab specimens are compromised for any reason or questionable accuracy of the result. Safety labs will then be repeated (amount of blood drawn not to exceed 15 mL).

Medication changes and adverse events collected through out subjects' participation.

Special considerations in case of unforeseeable hardships such as public health emergencies or weather-related events.

In the event of subjects not being able to complete study visits for the reasons described above the following remedial steps will be taken:

- Visits #3,4, 6 and 7 can be completed via a phone interview during which the subject will answer the safety questionnaire (no changes in compensation).

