Oral Glucose Tolerance Test (OGTT): This procedure could cause possible nausea from glucose beverage. **DEXA and anthropometrics:** Radiation exposure during DEXA is equivalent to about two percent of the average radiation dose from all sources (natural background radiation, consumer appliances, radon gas, medical tests, etc.) that a person in the United States receives each year. Subjects who have participated in any other research study or medical procedure involving significant ionizing radiation exposure (e.g., multiple chest x-rays) in the past 12 months will be excluded. For female subjects, a urine pregnancy test is administered before the DEXA. Body weight is measured to the nearest 0.1 kg and height to the nearest 0.1 cm.

Amiloride therapy: In previous clinical trials with higher doses (10 mg) amiloride was well tolerated. Nevertheless, our team of investigators is well aware of the potential side effects (1-10%): dizziness, fatigue headache, hyperkalemia. Subjects will be closely monitored during the drug/placebo treatment intervention. After each safety visit, [name] and [name] will review blood pressure and heart rate readings, as well as results of renal function and electrolyte levels. The treatment will be discontinued in case of hyperkalemia > 5.5 mEq/L, creatinine increases more than 30% above baseline, hypotension or severe dizziness. If the subject exhibits hyperkalemia or if creatinine increases more than 30% above baseline, the study team will repeat safety labs until they return to baseline. If a subject exhibits potassium > 5.5 mEq/L, creatinine increases more than 30% above baseline, hypotension or severe dizziness on the 5 mg dose, medication will be held for 1 week and a lower dose of amiloride will be started (half of a 5mg tablet). Once the dose of half of a 5mg tablet has been started, a safety visit will be completed 1 week later. If no clinically significant abnormalities are documented, safety visits will proceed as scheduled for the 5 mg dose. If there are clinically significant abnormalities

documented after down titration of amiloride, subjects will discontinue medication and participation in the clinical trial is terminated. In the event of a severe unexpected adverse event the subject will be unblinded to facilitate medical care.

Placebo: Pill Capsule: There is a potential risk for an allergic reaction to the gelatin capsule.

Placebo: Cellulose: These are no known risks.

Protection Against Risks

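### The written text does not say what governs restart when potassium or creatinine still meets a hold trigger at the end of the 1-week hold

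*Protocol*

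**What the plan says.** Protocol section II (Amiloride therapy) gives four instructions for overlapping triggers.

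- A standing hold: "The treatment will be held in cases of hyperkalemia > 5.5 mEq/L, creatinine increases more than 30% above baseline, hypotension or severe dizziness". No end point is stated.
- Laboratory follow-up for hyperkalemia or the creatinine rise: "the study team will repeat safety labs until they return to baseline". No interval, upper limit or link to restarting is stated.
- For the same triggers at 5 mg, restart is set by this sentence: "medication will be held for 1 week and a lower dose of amiloride will be started (half of a 5mg tablet". This ends on elapsed time alone.
- A check after restart: "Once the dose of a half of a 5mg tablet has been started, a safety visit will be completed 1 week later".

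Section VIII (Amiloride therapy) repeats the last three, including "Once the dose of half of a 5mg tablet has been started, a safety visit will be completed 1 week later", but replaces the standing hold with "The treatment will be discontinued in case of hyperkalemia > 5.5 mEq/L, creatinine increases more than 30% above baseline, hypotension or severe dizziness". It adds that clinically significant abnormalities after the step-down end both medication and trial participation.

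Section VII says "Additional Safety Visits/unscheduled visits might be scheduled in cases of down titration of amiloride dose". Section V lists as an exclusion "Potassium level > 5.0 mqE/L at time of screening". Figure 1 is captioned as a flow chart for managing side effects and adverse events, and it is not shown in the text available for review.

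**The concern.** Three sentences in section II decide what happens after a trigger, and each uses a different criterion. The standing hold depends on the current value, laboratory follow-up depends on recovery, and restart depends on the calendar. While labs recover within a week, the criteria agree. When they do not, the calendar sentence starts drug and the standing hold withholds it.

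Three things are at stake. First, the 1-week sentence has no exception, so taken alone it allows re-exposure while the value that caused the hold is still present. Second, two clinicians could handle the same participant differently, so time off drug and dose received would depend on which sentence was followed. Third, under section VIII a value that had never recovered before restart could be recorded as an abnormality after the step-down and end participation.

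**Working it through.** The plan states no figure on this point that could be reproduced. The check sets the sentences side by side on the protocol's own time intervals.

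**Inputs.** Potassium trigger above 5.5 mEq/L and creatinine trigger more than 30% over baseline (sections II and VIII); hold of 1 week (II and VIII); safety visit 1 week after the lower dose starts (II and VIII); screening potassium above 5.0 excluded (V); amiloride recruitment targets 34, 24, 24 and 24 (VI, Table 1); listed side effects at 1-10% (II and VIII).

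**Timeline.** Trigger and hold on day 0. Lower dose on day 0 + 7 = 7. First dated check on day 7 + 7 = 14. Repeat labs are required after day 0 but carry no date, and restart is not made to depend on their result.

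**What each sentence implies at day 7.** Screening excludes potassium above 5.0, so baseline will generally lie below the 5.5 trigger. That leaves three possible states:

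| Potassium at day 7 | 1-week sentence (II, VIII) | Standing hold (II) | Repeat-lab sentence (II, VIII) |
|---|---|---|---|
| Back at baseline | Start lower dose | No longer triggered | Repeats end |
| Above baseline, not above 5.5 | Start lower dose | No longer triggered | Repeats continue |
| Still above 5.5 | Start lower dose | Remain held | Repeats continue |

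- In the first row the sentences agree.
- In the second they can all be followed, with labs continuing on the lower dose. The text does not say whether a return to baseline was meant to come before restart.
- In the third the 1-week sentence and the standing hold cannot both be followed, and nothing says which prevails. The same holds for creatinine still more than 30% over baseline.

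In section VIII the standing hold is replaced by discontinuation. If that word means permanent stopping, it conflicts with the restart sentence in every row.

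**Illustration (hypothetical values).** Potassium is 5.9 at week 1 and 5.7 at week 2. The 1-week sentence starts the lower dose at week 2. The standing hold does not, because 5.7 > 5.5.

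**Size.** The number affected on amiloride is N × p × q, where N = 34 + 24 + 24 + 24 = 106, p is the proportion who meet a laboratory trigger and q is the proportion of those still meeting it at day 7. The documents give neither p nor q. Taking the listed 1-10% in place of p for hyperkalemia gives 106 × 0.01 = 1.1 to 106 × 0.10 = 10.6 before q is applied. Since q can lie anywhere from 0 to 1, the result runs from 0 to 10.6. This is a loose ceiling for the potassium trigger only: the 1-10% is not restricted to values above 5.5, and it says nothing about creatinine.

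**The case against.** The strongest reply is that the text never orders a restart above 5.5. The standing hold in section II has no time limit, so a repeat value still above the trigger can be read as extending the hold. The repeat-lab and restart sentences also govern different things and can usually be followed together. This stands in part. A reader might infer that the protocol instructs re-exposure. It does not; it fails to rule it out. What remains is that the 1-week sentence carries no exception and no precedence is stated.

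Figure 1 covers exactly this topic and may contain a restart condition. That stands, and it limits the point to a conflict in the written text. If the figure has a condition, sections II and VIII should match it.

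The investigator reviews potassium and renal function after each safety visit, and a safety officer reviews reports for corrective action (section XII). These are real safeguards, but neither is a stated criterion for restart.

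Four further inferences are tempting and not supported:

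- That sites would diverge. Section XIII lists multiple sites as not applicable; inconsistency could arise only between clinicians or occasions.
- That about 1 to 11 participants are affected. That range reflects any one listed side effect. Fatigue and headache are not hold triggers, and non-recovery at day 7 is not covered.
- That early restarts would cause avoidable exits mainly on amiloride. This is plausible for a drug with hyperkalemia as a listed effect, but the documents give nothing from which to estimate it.
- That section VII makes the post-restart visit optional. Its looser verb can be read as saying that such visits arise only if a step-down happens, which fits the firm 1-week visit in sections II and VIII.

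**Conclusion.** The point holds for the written text. For a participant whose labs still meet a hold trigger at day 7, the hold, repeat-lab and restart sentences do not give one answer, and the next dated check is a week after restart. This is more than missing detail, because the 1-week rule followed as written allows drug to restart while a trigger is still met. The group concerned is limited to those unrecovered at day 7; its size is unknown and probably small. The sample size and the SAP model are not affected.

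The conclusion rests on two assumptions: that Figure 1, which could not be seen, does not already settle the matter in a way the text is meant to follow; and that baseline potassium generally lies below 5.5, as the screening limit suggests. Because of the first, confidence is moderate. No view is taken on which rule is clinically right.

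**What to change.** Reconcile the hold, repeat-lab and restart sentences in protocol sections II and VIII with each other and with Figure 1. In the same edit, settle whether the triggers lead to treatment being held or discontinued. The result should be one rule stating what governs restart (elapsed time, the repeat-lab result, or both) and what happens when labs have not recovered at 1 week. As a minor edit, align the section VII wording on additional visits with the visit due 1 week after restart. The study physician and safety officer should choose the rule.

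The SAP is dated November 2025 and written in the past tense, so treatment may already be complete. If so, the sponsor should document which rule was applied to each participant whose drug was held.

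The cost is wording in three sections and a check of the figure; the repeat labs are already planned. Depending on the rule chosen, some participants may stay off drug longer.

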BIOMEDICAL RESEARCH PROTOCOL UNIVERSITY OF MISSOURI

Project Title: Estrogen receptor alpha signaling in endothelial cells exacerbates arterial

stiffening via upregulation of ENaC in insulin resistant females

IRB Number: 2012990 Version Number: 24

Version Date: October 30, 2023

Principal Investigator: [name]

Funding Source: NHLBI

Clinical Trial Phase: Phase II

Clinicaltrials.gov Number: NCT03837626 Study Drug/Study Device: *Amiloride*

I. Research Objectives/Background

Hypothesis: Estrogen action, through the endothelial cell (EC) estrogen receptor alpha (ERα) upregulates EC ENaC expression and activity exacerbating endothelial and arterial stiffening in overweight and obese, insulin resistant (IR) premenopausal females. The corollary to this hypothesis is that ENaC inhibition will have a greater impact on arterial stiffness in overweight and obese, premenopausal insulin resistant women than in overweight and obese IR postmenopausal women or age matched obese IR men.

To test our hypothesis, we will use in vivo measures of endothelial function and arterial stiffness in a cohort of overweight and obese IR subjects treated with amiloride, an ENaC inhibitor, to accomplish the follow aim:

To determine whether treatment with the ENaC inhibitor, amiloride, improves endothelial function and arterial stiffness in overweight and obese IR subjects in a randomized placebo-controlled trial examining pre and postmenopausal women and age-matched men.

II. Drugs/Biologics/Devices

Following screening, male and female subjects will be randomized to a doubled blinded placebo control trial. Subjects will start on either a 24-week treatment with oral medication, either amiloride, a max dose of 5 mg daily, or placebo intervention.

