- Visit #1: Vital signs (blood pressure and heart rate), weight, DEXA, assessment of brachial and popliteal artery flow-mediated dilation (FMD), cfPWV, femoral artery blood flow, and oral glucose tolerance test (OGTT) (amount of blood drawn not exceeding 55 mL). OGTT will be done when glucose beverage is available. Entire visit is expected to take up to 6 hours. Women of childbearing age will undergo a pregnancy test prior to the DEXA scan and excluded if pregnancy is confirmed. Subject is dispensed the bottle of study drug/placebo and instructed how to take them.
- Visit #2 (1 week after starting the medication +6 days/-2 days): Vital signs, safety questionnaire for side effects, and blood draw for safety laboratories (basic metabolic panel). Entire visit is expected to take up to 30 minutes.
- Visit #3 (4 weeks after starting the medication +/- 6 days): Vital signs, safety questionnaire for side effects, and blood draw for safety laboratories (basic metabolic panel). Entire visit is expected to take up to 30 minutes.
- Visit #4 (8 weeks after starting the medication +/- 6 days): Vital signs, safety questionnaire for side effects, and blood draw for safety laboratories (basic metabolic panel). Entire visit is expected to take up to 30 minutes. If the prior safety visit labs have been within the protocol parameters this visit may be completed as a phone call visit to collect safety questionnaire for side effects and any changes in the subject's health.
- Visit #5 (12 weeks after starting the medication +/- 6 days): Vital signs, weight, DEXA, safety questionnaire for side effects, and blood draw for safety laboratories (basic metabolic panel) and general biochemistries. Subject also will have assessment of brachial and popliteal artery FMD and cfPWV. Women of childbearing age will undergo a pregnancy test prior to the DEXA scan and withdrawn from study if pregnancy is confirmed. Subject will be dispensed a new bottle of study drug/placebo. Entire visit is expected to take up to 3 hours.
- Visit #6 (16 weeks after starting the medication +/- 6 days): Vital signs, safety questionnaire for side effects, and blood draw for safety laboratories (basic metabolic panel). Entire visit is expected to take up to 30 minutes. If the prior safety visit labs have been within the protocol parameters this visit may be completed as a phone call visit to collect safety questionnaire for side effects and any changes in the subject's health.

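### Menopausal status stands in for estrogen exposure, but systemic estrogen therapy is neither excluded, recorded as a factor nor analysed, so users dilute the pre/postmenopausal contrast

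*Protocol*

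**What the plan says.** For ENaC inhibition, Protocol section I predicts a "greater impact on arterial stiffness in overweight and obese, premenopausal insulin resistant women than in overweight and obese IR postmenopausal women", and attributes the difference to estrogen acting through its receptor in endothelial cells.

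Section VI turns this into planning figures for carotid-femoral pulse wave velocity (cfPWV). Table 1 reads "1. Premenopausal women 7.2> 6.2 1.2 90% 0.05 30 34 17" and "4. Postmenopausal women 8.0> 7.5 0.5 90% 0.05 21 24 12": a fall of 1.0 m/s with SD 1.2 before menopause, and of 0.5 m/s with SD 0.5 after it. The smaller postmenopausal response is expected "given a lesser contribution of estrogen signaling in the activation of ENaC in this population". The larger premenopausal SD is put down to "greater variation in the response of premenopausal women due to the effects of reproductive hormones".

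Postmenopausal status is defined in section VI by six months without menses and nothing else. None of the 14 exclusions in section V mentions estrogen or menopausal hormone therapy. Exclusion 10 rules out women who use no contraceptive, without separating hormonal from other methods. Section VII has medication changes collected during participation, but gives them no role in the analysis. The SAP model contains time, group and their interaction, with no term for menopausal status or hormone use.

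The outcome visits after baseline are set by time on study drug alone: "Visit #5 (12 weeks after starting the medication +/- 6 days" and "Visit #8 (24 weeks after starting the medication +/- 6 days".

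**The concern.** The inference about estrogen comes from comparing the amiloride effect in two strata that are supposed to differ in estrogen exposure. A postmenopausal woman on systemic estrogen meets the six-month definition and is correctly classified, yet she does not have the low exposure for which that stratum was chosen. If estrogen modifies the response as the protocol supposes, her response moves towards the premenopausal one. The observed difference between strata then understates the difference due to estrogen, and a finding of no difference between menopausal groups becomes harder to interpret. Nothing in the SAP would show whether this had happened.

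**Working it through.** **Inputs (Protocol section VI, Table 1).** Premenopausal: change 1.0 m/s, SD 1.2, targets 34 amiloride and 17 placebo. Postmenopausal: change 0.5 m/s, SD 0.5, targets 24 and 12. Alpha is 0.05, taken as two-sided because sidedness is not stated.

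**1. The plan's own figure.** For a 1:1 two-sample comparison at 90% power, n per arm = 2 × [SD × (1.960 + 1.282) / Δ]².
- Premenopausal: 2 × (1.2 × 3.242 / 1.0)² = 30.26; Table 1 gives 30.
- Postmenopausal: 2 × (0.5 × 3.242 / 0.5)² = 21.01; Table 1 gives 21.

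Table 1 is reproduced. It sizes the change within each group; neither it nor the text sizes the contrast between menopausal groups.

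**2. The contrast as planned.** Taking the Table 1 changes as placebo-adjusted effects, the difference is 1.0 − 0.5 = 0.5 m/s.
- SE = √[1.2² × (1/34 + 1/17) + 0.5² × (1/24 + 1/12)] = √(0.1271 + 0.0313) = 0.398 m/s.
- Power = Φ(0.5/0.398 − 1.96) = 24%.

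**3. Dilution by estrogen users.** Assume a share p of postmenopausal women use systemic estrogen and respond by 1.0 instead of 0.5 m/s. The postmenopausal mean effect is 0.5(1 − p) + 1.0p = 0.5 + 0.5p, and the contrast is 1.0 − (0.5 + 0.5p) = 0.5(1 − p). The SE is held at 0.398.

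| p (assumed) | Contrast (m/s) | Power, placebo-adjusted |
|---|---|---|
| 0 | 0.50 | 24% |
| 10% | 0.45 | 20% |
| 20% | 0.40 | 17% |
| 30% | 0.35 | 14% |

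If only the amiloride arms were compared, SE = √(1.44/34 + 0.25/24) = 0.230, and power would be 59%, 50% and 33% at p = 0, 10% and 30%.

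**4. What the restricted contrast costs.** Leaving out a share p of the 36 postmenopausal women, equally from both arms, multiplies the second variance term by 1/(1 − p) and restores the contrast to 0.5.
- p = 10% (about 4 women): SE = √(0.1271 + 0.0313/0.9) = 0.402; power 24%.
- p = 30% (about 11 women): SE = √(0.1271 + 0.0313/0.7) = 0.414; power 23%.

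The precision lost is small because the premenopausal term dominates the variance.

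**5. Cycle phase.** Weeks 12 and 24 are days 84 and 168. With cycle length L, the distance to the nearest day matching the baseline cycle day is the smaller of (days mod L) and L − (days mod L).
- L = 28: 0 and 0 days. L = 27 or 29: 3 and 6 days.
- L = 26 or 30: 6 and 12 days. L = 25: 9 and 7 days. L = 32: 12 and 8 days.

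For cycle lengths from 24 to 35 days, the ±6-day window reaches the matching day at both visits only when L is 27, 28 or 29.

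**The case against.** **Size.** Neither the share of users nor their response is in the documents. At 10% use the contrast moves by 0.05 m/s against an SE of 0.40, and at about 24% power the contrast is weak with or without the fix. This stands: the point concerns what the contrast measures, and the fix does not rescue power. If users responded no differently from other postmenopausal women, there would be no dilution.

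**Randomisation.** A reader might infer that the amiloride–placebo comparison is biased. It is not: randomisation protects that comparison on average. Only the comparison between menopausal groups is affected.

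**Hormonal variation is already budgeted.** The SD of 1.2 and the larger premenopausal targets allow for it. That is fair for the premenopausal group, but nothing allows for estrogen users in the postmenopausal group.

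**The stronger reading on cycle phase.** From Table 1 a reader might infer that hormones account for 1.2² − 0.5² = 1.19 of 1.44, or 83%, of the premenopausal variance, and that aligning visits to the cycle would remove much of it. The documents do not support this. These are planning SDs, and the text speaks of variation in response, which may mean that women differ in their response to the drug; alignment would not remove that. The planned premenopausal change is also twice as large: if SD scaled with it (0.5 to 1.0), only 1.44 − 1.00 = 0.44 (31%) would remain to be explained. Some contraceptive users may have no natural cycle, and the ±6-day window rarely reaches the matching day.

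**Data and timing.** The telephone and Qualtrics medication answers are expressly not study data, and the screening visit lists medical history without naming medications, so a baseline record is not certain. But exclusions 4 and 12 cannot be applied without reviewing medications, so source records should hold the information. The SAP, dated November 2025, is in the past tense, which suggests that visits can no longer be rescheduled.

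**No contrast in the SAP.** The SAP says that only two groups were compared and specifies no menopausal contrast. This stands as a gap of its own; the contrast has to be written down before a restricted version of it means anything.

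**Conclusion.** The concern holds for systemic estrogen therapy. The documents use menopausal status as the proxy for estrogen exposure and contain no provision for postmenopausal women whose exposure is raised by treatment. The consequence is dilution of the planned 0.5 m/s contrast to 0.5(1 − p), for example 0.45 at 10% and 0.35 at 30%, with placebo-adjusted power falling from about 24% to 20% and 14%. This rests on an assumed p, on users responding like premenopausal women, on the Table 1 effects and SDs, and on full recruitment. The direction follows from the protocol's own hypothesis; the size is unknown.

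Cycle phase is secondary. The visits ignore it, and it may add noise in naturally cycling women, but its contribution to the SD of 1.2 cannot be derived from the documents.

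**What to change.** 1. State the placebo-adjusted pre/postmenopausal contrast in the SAP. Flag systemic estrogen use at baseline from the medication review that exclusions 4 and 12 require; if it was not captured as study data, abstract it from source records.
2. Report that contrast in all randomised women and, beside it, with postmenopausal baseline users left out. Give the number of users by arm.
3. Describe estrogen use started during the trial, but do not exclude on it, because it arises after randomisation.
4. Align visits by cycle phase only if visits are still being scheduled. Otherwise, where dates of menses exist, use cycle phase only as an exploratory covariate.

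**Cost:** some abstraction work, one additional contrast, and slightly fewer postmenopausal women in it (SE 0.40 to 0.41 m/s even if 30% are left out). No new procedure is needed. If the results have already been seen, label the restricted contrast as post hoc.
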